4.3 Subject Identification

After having signed their written informed consent, the subjects will be allocated an Identification Number (Subject ID).

Once the subject satisfies to all inclusion/non-inclusion criteria, they will be included in the study.

This Subject ID will be unique and will contain 6 digits: the first two digits corresponding to the country number, the following two digits corresponding to the site number, which are attributed at the beginning of the study, and the last two digits being chronologically implemented depending on subject enrollment. The lowest enrollment number will correspond to the first subject enrolled at this site and the highest number to the last subject enrolled.

 CONFIDENTIAL	Protocol No. GDX-44-008 Version No.4.0 including amendments 1 and 2 12 December 2017	Page 28 / 64
---	--	--------------

5. INVESTIGATIONAL MEDICINAL PRODUCTS

Investigational Medicinal Product(s) (IMPs) will be manufactured, labeled, packaged and released in accordance with:

- European Directive 2003/94/EC laying down the principles and guidelines of Good Manufacturing Practice in respect of Medicinal Products for human use and Investigational Medicinal Products for human use
- EudraLex, The Rules Governing Medicinal Products in the European Union, Volume 4, EU Guidelines to Good Manufacturing Practice - Medicinal Products for Human and Veterinary Use, Annex 13 Investigational Medicinal Products

In addition, the IMP manufacturing, packaging, labeling and release will comply with any local applicable regulatory requirement.

The IMP will consist of an individually packaged vial in a carton box with a single use detachable label that will allow ensuring accuracy of IMP allocation per subject.

5.1 Investigational Medicinal Product: P03277

Name: P03277 [REDACTED]

Pharmaceutical form: vial of 20 ml

P03277 is an aqueous solution. Each vial contains 20 mL of solution presented as a sterile, clear, yellow, ready-to-use solution for injection.

Concentration: 0.5 M

P03277 dose per administration:

- 0.1 mmol/kg BW (corresponding to 0.2 mL/kg body weight) for the first cohort (30 subjects),
- 0.05 mmol/kg BW (corresponding to 0.1 mL/kg body weight) for the second cohort (10 subjects).

P03277 will be injected via a peripheral vein (the antecubital vein is preferred). The IV injection line will consist of a large bore indwelling catheter (at least 18 gauge).

Sufficient IMP must be allocated to one subject according to his/her body weight.

Route and method of administration: by intravenous (IV) bolus injection at 2 mL/s rate without dilution, followed by a 0.9% saline flush at same rate to ensure complete injection of the contrast medium.

The P03277 administration is to be performed by power injector in order to better control injection rate.

Please refer to the Investigator Brochure for more information on P03277.

5.2 Packaging, Labeling, Storage

Packaging and labeling will be performed in strict accordance with the local regulatory specifications and requirements.

The packaging and labeling of P03277 will be performed by Guerbet (or its designee).

 CONFIDENTIAL	Protocol No. GDX-44-008 Version No.4.0 including amendments 1 and 2 12 December 2017	Page 29 / 64
---	--	--------------

In addition to the usual and regulatory labeling for clinical studies, each IMP will have a white detachable sticker indicating the protocol number, IMP number and other locally required information. This label will be stuck on the subject file or study documentation.

IMP will consist in a box that contains one 20 ml vial of P03277

All IMPs will be stored in a secure place, under the responsibility of the Investigator or other authorized individuals. The IMPs should be stored at a temperature of 25°C or below in the original package, protected from light and not frozen.

At the time of the study completion, all used (including empty vials) and unused IMPs should have been returned to the Sponsor or to the predefined location for storage before destruction.

5.3 Condition of Investigational Medicinal Product Allocation

5.3.1 *Investigational Product(s) Allocation / Randomization*

Since the study design is open label, IMP will not be allocated by randomization. Sufficient IMP(s) will be assigned to each investigational site. The Investigator will use the IMP with the lowest IMP number available at the site (chronological assignment). This number will be independent from the subject's identification number.

5.3.2 *Double-Blind Conditions*

Not applicable

5.3.3 *Individual Study Treatment Unblinding*

Not applicable

5.4 Investigational Medicinal Product Management

The investigator, the hospital pharmacist, or other personnel allowed to store and dispense Investigational Medicinal Product(s) is responsible for ensuring that the IMP used in the clinical study is securely maintained as specified by Guerbet and in accordance with the applicable regulatory requirements.

Any quality issue noticed with the receipt or use of an IMP (deficient IMP in condition, appearance, pertaining documentation, labeling, expiry date, etc.) should be promptly notified to Guerbet, who will initiate a complaint procedure.

Under no circumstances shall the investigator supply IMP to a third party, allow the IMP to be used other than as directed by this clinical study protocol, or dispose of IMP in any other manner.

If during the administration of IMP, the subject experiences a Serious Adverse Event (SAE), the IMP administration must be discontinued and the subject rendered emergency medical care and monitored until the event is resolved (see section 10.2)

5.5 Non Investigational Medicinal Product(s) and Other Study Products

Not applicable

Guerbet  CONFIDENTIAL	Protocol No. GDX-44-008 Version No.4.0 including amendments 1 and 2 12 December 2017	Page 30 / 64
--	--	--------------

5.6 Study Product(s) Compliance and Accountability

The investigator, the hospital pharmacist, or other allowed personnel will keep accurate records of Investigational Medicinal Products accountability at site level as well as accurate records of the batch numbers and quantities of the IMP given to each subject.

The dosing information will be recorded in individual subject's records. When protocol required IMP administration conditions are not followed, reason(s) will be given and recorded by the investigator.

 CONFIDENTIAL	Protocol No. GDX-44-008 Version No.4.0 including amendments 1 and 2 12 December 2017	Page 31 / 64
--	--	--------------

6. CONCOMITANT TREATMENTS

6.1 General considerations

Any medication, including contraception, homeopathic products, over-the-counter medications, as well as prescription drugs, on-going at the time of subject's informed consent signed or administered during the study will be recorded in the subject CRF until safety follow-up visit (Day+1). The following information must be provided:

- Drug (brand name or generic name)
- Route of administration
- Purpose (Medical history/study disease/ AE/Premedication/contraception/Prophylaxis)
- Indication
- Duration of treatment

6.2 Concomitant Treatments of Special Attention

In order to limit any interference with the safety and efficacy evaluation of Investigational Product, the following precaution and restriction must be considered:

Currently, no treatment has been identified that is capable of preventing an allergic reaction with any gadolinium-based contrast agents. Thus, no pre-treatment of any nature will be recommended before contrast-enhanced MRI. Nevertheless, if the investigator decides to premedicate a subject, the treatment must be documented in the medical file and then in the CRF.

In general, there are no specific recommendations regarding Gadolinium-Based Contrast Agents, and therefore, no specific hydration procedure is defined in this protocol. Nonetheless, whenever possible, the subject should be encouraged to drink water and other non-alcoholic fluids liberally before and after the injection.

According to current knowledge, there is no other concomitant treatment of special attention in that study. However warnings and precautions for use of the concomitant treatments taken by the subject should be considered.

6.3 Prohibited Concomitant Treatments

Any other contrast agent should not be administered with 7 days before and 3 days after P03277 administration.

7. EVALUATION CRITERIA

An overview of the efficacy variables is provided in the Table 1: Overview of efficacy variables below.

Table 1: Overview of efficacy variables

Variables	On-going on-site Reading	Expert Reading
Primary efficacy variables		
Nodule diagnosis		✓
Secondary efficacy variables		
Technical adequacy of images	✓	✓
Number of nodules detected	✓	✓
Qualitative evaluation (nodule intensity, presence of intranodule iron and fat and visualization of perilesional capsule)		✓
Visualization of biliary and liver vascular abnormalities		✓
Qualitative evaluation at available very delayed image, liver enhancement relative to the unenhanced fat-suppressed GRE T1 sequence and nodule signal enhancement relative to parenchyma		✓
Quantitative evaluation	✓	
SI measurements in nodules, liver, background, aorta and the portal vein for SNR CNR PE		

7.1 Primary Criterion

For evaluation of **diagnostic value (defined as Sensitivity and Specificity) of P03277 for HCC** the following will be assessed:

Primary criteria:

- **Nodule diagnosis at P03277 imaging** (HCC, not HCC specify) will be assessed:
 - on a maximum of 3 hepatic nodules per subject
 - Based on visual qualitative analysis of P03277 triphasic imaging (arterial, portal and delayed phases) showing HCC typical hallmarks according to EASL/EORTC criteria (arterial hypervascularization and portal wash-out or delayed wash-out)
 - by two expert readers. In case of discordance, a consensus diagnostic will be obtained
- **The standard of reference** for diagnosing liver nodules (HCC, other malignant, regenerative or dysplastic nodule, benign, uncertain) will be given by the site according to their standard of care and according to adapted EASL/EORTC diagnostic criteria, considering previous contrast enhanced imaging (CT and/or MRI) and/or histology analysis and/or the more recent AFP results available:

HCC will be considered when:

- Histology is positive for HCC
- Or Nodule identified and characterized by typical features using two different triphasic contrast enhanced modalities. Typical features are arterial hypervascularization and portal wash-out or delayed wash-out

 CONFIDENTIAL	Protocol No. GDX-44-008 Version No.4.0 including amendments 1 and 2 12 December 2017	Page 33 / 64
---	--	--------------

- Or AFP>200ng/mL in a presence of a single nodule
 Other diagnosis than HCC could be based on imaging only and/or histology.

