4. SUBJECT SELECTION

4.1 Inclusion Criteria

1. Female or male adult subject aged at least 18 years old or older (subject having reached legal majority age).
2. Subject able and willing to participate to the study.
3. Subject having read the information and having provided his/her consent to participate in writing by dating and signing the informed consent prior to any study related procedure being conducted.
4. Subject presenting with liver cirrhosis or chronic liver disease as shown by previous liver biopsy or by combination of clinical, endoscopic, biological, ultrasound parameters, and elastography
5. Subject presenting with one to a maximum of 3 untreated hepatic nodule(s) of less than or equal to 3 cm (long axis) previously identified and/or characterized through enhanced CT and/or MRI within a maximum of 21 days before P03277 imaging, confirmed for HCC or not
6. Female subject must be using a medically approved contraception method* detailed below or be surgically sterilized or post-menopausal (>12 months amenorrhea)

**medically approved contraception methods include: female sterilization, barrier methods of contraception (condom or occlusive cap (diaphragm or cervical/vault caps) with spermicidal foam/film/cream/ vaginal suppository), use of oral, injected or implanted hormonal methods of contraception or other forms of hormonal contraception that have comparable efficacy (failure rate <1%), for example hormone vaginal ring or transdermal hormone contraception, placement of an Intrauterine Device (IUD) or Intrauterine System (IUS).*

7. Subject affiliated to national health insurance according to local regulatory requirement

To be selected and included in the study, the subject must meet all these inclusion criteria.

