12.3 Efficacy Data

Efficacy data will be summarized and presented by dose using the FAS and PP set for primary efficacy analysis and only using FAS for any other efficacy analysis.

Primary efficacy analysis

First of all, results of **examinations results used for standard of reference** will be presented: at subject level showing number and frequency of AFP results by category ($>200\text{ng/mL}$ or $\leq200\text{ng/mL}$) and by number of nodules for a subject (multiple or single nodule), previous contrast enhanced imaging modalities (CT and/or MRI), timelines and type of contrast agent category for MRI. At nodule level, typical imaging hallmark obtained by nodule (CT and/or MRI) and intensity of parenchyma relative to the nodule at each available phase will be presented. Timelines for biopsy (or surgical specimen collection) will be presented at subject level and nodules histology results (HCC, other malignant, regenerative or dysplastic nodule, benign, uncertain) will be presented at nodule level.

P03277 imaging diagnosis (HCC and not HCC) will be presented at nodule level displaying number and frequency for each standard of reference group HCC or not HCC according to the **Table 2**.

Table 2 : Diagnostic value evaluation for HCC

		P03277 imaging expert reading results			
		HCC: (Typical features on this MR examination)	Not HCC (No nodule/atypical features)		
Standard of reference	HCC:	True positive $n1$	False negative $n3$	Total $n1+n3$	
	Not HCC including uncertain cases	False positive $n2$	True negative $n4$	Total $n2+n4$	
		Total $n1+n2$	Total $n3+n4$	All total $N+$	

The following parameters will be calculated:

Sensitivity: the number of nodules showing true positive HCC divided by all nodules considered HCC according to standard of reference ($n1 / n1+n3$)

Specificity: the number of nodules showing true negative HCC divided by all nodules considered as not HCC or uncertain as standard of reference ($n4 / n2+n4$)

Accuracy: the number of nodules showing true positive HCC and true negative HCC over all nodules ($n1+n4 / N+$)

Positive predictive value: the number of nodules showing true positive HCC /all nodules showing HCC according to P03277 imaging ($n1 / n1+n2$)

Negative predictive value: the number of nodules showing true negative HCC /all nodules not showing HCC according to P03277 imaging ($n4 / n3+n4$)

 CONFIDENTIAL	Protocol No. GDX-44-008 Version No.4.0 including amendments 1 and 2 12 December 2017	Page 51 / 64

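### Table 2 counts reference-uncertain nodules as not HCC, so a true HCC that meets none of the three reference routes leaves sensitivity, and a correct P03277 call on it scores as a false positive

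*Protocol*

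**What the plan says.** **The reference standard (section 7.1).** The site labels each nodule HCC, other malignant, regenerative or dysplastic, benign, or uncertain. HCC is accepted by any of three routes:

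- positive histology;
- a nodule "characterized by typical features using two different triphasic contrast enhanced modalities", where "Typical features are arterial hypervascularization and portal wash-out or delayed wash-out";
- AFP above 200 ng/mL when there is only one nodule.

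For the remaining labels, "Other diagnosis than HCC could be based on imaging only and/or histology". The expert P03277 read uses the same hallmark to call HCC.

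**What is available to reach a route.** Under section 4.1 nodules need only be "previously identified and/or characterized through enhanced CT and/or MRI", so one modality is enough for entry. The visits in section 9.1 schedule no second reference modality. Section 9.1.4 makes biopsy or resection optional.

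**The scoring (section 12.3).** The reference-negative row of Table 2 reads "Not HCC including uncertain cases". Sensitivity is "the number of nodules showing true positive HCC divided by all nodules considered HCC according to standard of reference". Specificity is "the number of nodules showing true negative HCC divided by all nodules considered as not HCC or uncertain as standard of reference".

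**The concern.** The two sections interact. Section 7.1 sets a demanding rule for calling a nodule HCC. Section 12.3 treats every nodule that does not pass it as if HCC had been ruled out, including those the site could not classify. An HCC that was typical on the only modality done, or atypical on both, with no histology and no qualifying AFP, is then scored the wrong way round: P03277 is penalised for finding it and credited for missing it.

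Two effects follow, and they differ in kind. For specificity and PPV this is misclassification by the reference standard. For sensitivity it is selection: HCCs verified by imaging alone are those already typical on CT or MRI, by the same hallmark the P03277 readers apply.

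Sensitivity and specificity are the primary result (sections 2.1 and 7.1). Section 1 also raises the possibility that P03277 characterises small atypical HCC better. If it does so in an unverified nodule, the primary table records an error.

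**Working it through.** **Tracing one nodule.** Take a true HCC with no histology, the hallmark on fewer than two modalities, and no single-nodule AFP above 200 ng/mL. It meets none of the three routes in 7.1, so under the listed criteria it is labelled uncertain or given another diagnosis on imaging. Either label puts it in the second row of Table 2:

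| P03277 read | Cell in Table 2 | Correct in truth? |
|---|---|---|
| HCC | n2, false positive | yes |
| Not HCC | n4, true negative | no |

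In neither case is it in n1 + n3.

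**Other rules that might remove it.** The FAS (12.1) requires a completed standard of reference, but uncertain is one of the permitted reference labels. Section 11.2 discontinues and replaces subjects whose reference examination is not available; a completed uncertain label is not that case. Section 8 foresees negatives proven as non-HCC or uncertain after biopsy, but 9.1.4 does not require the biopsy.

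**The plan's own figure.** Section 8 expects about 66% HCC among the 30 subjects of the first cohort: 0.66 × 30 = 19.8, so about 20 HCC and 10 negative or uncertain. No precision calculation is stated.

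**Illustration.** Assumed: one nodule per subject; D = 20 reference HCC, of which TP = 18 are called HCC; N = 10 in the reference-negative row; f = 1 false positive among the true non-HCC; h = 2 of the 10 are unverified HCC, of which P03277 calls c HCC.

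- Reported sensitivity = TP/D = 18/20 = 0.900
- Sensitivity counting them = (TP + c)/(D + h) = (18 + c)/22
- Reported specificity = (N − f − c)/N = (9 − c)/10
- Specificity without them = (N − h − f)/(N − h) = 7/8 = 0.875

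| c | Reported specificity | Without them | Reported sensitivity | Counting them |
|---|---|---|---|---|
| 0 | 0.900 | 0.875 | 0.900 | 0.818 |
| 1 | 0.800 | 0.875 | 0.900 | 0.864 |
| 2 | 0.700 | 0.875 | 0.900 | 0.909 |

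The large sensitivity error (c = 0) and the large specificity error (c = 2) belong to different rows and cannot occur together. With h = 0 both errors vanish.

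**Cross-check with other inputs.** Use the sensitivity of 0.820 and specificity of 0.934 that section 1 cites for extracellular agents, and assume that 10% of 19.8 true HCCs (1.98) are unverified. Expected reported specificity is (10.2 × 0.934 + 1.98 × 0.18)/(10.2 + 1.98) = 0.811. At 20% and 30% unverified it is 0.723 and 0.657. If P03277 detects only half of the unverified HCCs, the three values are 0.863, 0.813 and 0.774; reported sensitivity stays at 0.82, while sensitivity over all HCCs is 0.788, 0.756 and 0.724.

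**Sampling error.** The exact 95% interval is 0.555 to 0.997 for 9/10 and 0.348 to 0.933 for 7/10. The second contains 0.875.

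**The case against.** The strongest reply is that pooling is an open and consistent choice. It appears in Table 2, in the specificity formula, in the planning text of section 8 and in the secondary analyses. The study is exploratory, plans no test and admits the limits of its size. Section 12 defers the full methods to the SAP, where breakdowns by subgroup normally sit. Section 12.3 already tabulates the prior hallmark and histology by nodule, and 12.1 plans individual listings.

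Much of this stands. There is no contradiction in the text, the shifts are within sampling error, and the mix of reference routes will be visible. But the row and both denominators are fixed in the protocol itself, so the point is not something left to the SAP. Misclassification does not shrink with more subjects as sampling error does. And 12.3 does not cross the prior hallmark or the histology with the P03277 read, so it would not show which false positives were unverified nodules.

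A reader might infer more than the protocol supports:

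- *Incorporation bias, because test and reference share a hallmark.* Section 9.1.3 excludes P03277 images from the Day +1 reference diagnosis.
- *All atypical HCC is lost from sensitivity.* Atypical HCC verified by histology or by AFP does count.
- *A bias of 10 points, or about 33 in the second cohort.* Those steps, 1/10 and 1/3 (the latter if a 7/3 split holds there), are what any single read moves specificity by. They measure cell size, not bias.

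**Conclusion.** The point holds as a flaw in how the primary table is scored: sections 7.1 and 12.3 together can make reported specificity and PPV wrong, and can tilt sensitivity toward HCC already typical on CT or MRI. The direction depends on the P03277 read. Calling the unverified HCCs lowers specificity; missing them raises it slightly and leaves sensitivity overstated.

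The size is unknown and may be zero. The 0.700 against 0.875 rests entirely on assumed counts: 10 reference negatives, one other false positive, and two unverified HCCs both called HCC. It also takes the listed criteria as applied; the site assigns the reference by its standard of care and might label some such nodules HCC. The protocol gives no ground for saying that the primary result will be wrong by any particular amount. This is a cheap improvement to an exploratory study, not a reason to replace its primary analysis.

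**What to change.** In section 12.3, keep pooled Table 2 as the primary analysis and add:

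1. Uncertain nodules as their own row against the P03277 read, with specificity, accuracy, PPV and NPV repeated without them. Sensitivity does not change. In the illustration with c = 2 and both nodules labelled uncertain, specificity goes from 7/10 = 0.700 to 7/8 = 0.875, accuracy from 25/30 = 0.833 to 25/28 = 0.893 and PPV from 18/21 = 0.857 to 18/19 = 0.947. NPV stays at 7/9 = 0.778.
2. Table 2 as counts by reference route. For HCC: histology, two-modality imaging, AFP. For not HCC: histology, imaging only. State in advance which row takes a nodule that meets more than one route.

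The cost is a few descriptive tables from data already collected per nodule or per subject (sections 9.1.1 and 9.1.4), with no new procedure.

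The limits should be stated with the tables. Strata will be small within each dose. Dropping uncertain nodules also drops some true non-HCC. It does not catch an HCC given another diagnosis on imaging alone: if both nodules in the illustration were labelled that way, specificity would stay at 0.700, and only the imaging-only row would mark them as lacking histology. The tables are descriptive and show the bias without removing it.

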7.2 Secondary Criteria

7.2.1 Efficacy assessments of P03277 imaging

- **Technical adequacy of images** (*ongoing on-site and expert reading*) will be assessed as adequate, yes or no and reason for inadequacy will be recorded using-a 5 items (1= Artifacts due to subject , 2 = Artifacts due to machine, 3 = Artifacts due to contrast agent, 4 = Injection technical failure, 5 = Other, specify)
- **Visualization of biliary and liver vascular abnormalities** (*expert reading*) will be described: presence of portal thrombosis, hepatic venous thrombosis, biliary tract invasion, and visualization of arterio-portal fistula.
- **Number of nodules detected** (*ongoing on-site and expert reading*)
- **Qualitative evaluation** (*expert reading*)
 - At each phase (T2, T1 unenhanced, arterial, portal, delayed, 15 ±5 minutes): nodule (maximum of 3) intensity relative to parenchyma according to the scale: hypointense, hyperintense or isointense (and relative to spleen on T2 if hyperintense); In addition nodules will be described as homogeneous or heterogeneous
 - Presence of fat and Iron within the liver nodules at unenhanced phase in and opposed phase (intra nodule)
 - Visualization of a perilesional capsule (yes/no) at portal phase or delayed phase or at 15 ±5 minutes
- **Quantitative evaluation** (*ongoing on-site reading*)
 - At each phase, (T1 unenhanced, arterial, portal, delayed, 15 ±5 minutes) SI measurement on nodule (maximum of 3), liver, and background for SNR, CNR, and nodule percentage enhancement (PE)

Nodule SNR (Signal to noise ratio) will be calculated at each phase using the following formula: $SInodule/SDnoise$ where $SInodule$ is “nodule ROI intensity” and $SDnoise$ is “Background ROI: SD intensity”.

CNR (contrast to noise ratio) will be calculated at each phase using the following formula: $(SInodule-SIIliver)/ SDnoise$ where $SInodule$ is “nodule ROI intensity”; $SIIliver$ is “liver parenchyma ROI intensity” and $SDnoise$ is “Background ROI: SD intensity”.

PE (Nodule Percentage Enhancement) will be calculated using the following formula: $[(SIp\text{post}-SIp\text{pre})/SIp\text{pre}]*100$ where $SIp\text{post}$ is the nodule signal intensity at each phase (arterial, portal, delayed, 15 ±5 minutes) and $SIp\text{pre}$ is the nodule signal intensity at unenhanced sequence.

- On arterial and on portal phase, SI measurement of the aorta and the portal vein maximum vessel enhancement for SNR calculation purpose.

Vascular SNR (Signal to noise ratio) will be calculated using the following formula: $SIAorta/SDnoise$ where $SIAorta$ is “aorta ROI intensity” and $SDnoise$ is “Background ROI: SD intensity” at arterial phase, $SIPortal/SDnoise$ where $SIPortal$

 CONFIDENTIAL	Protocol No. GDX-44-008 Version No.4.0 including amendments 1 and 2 12 December 2017	Page 34 / 64
---	--	--------------

portal vein is “portal vein ROI intensity” and SDnoise is “Background ROI: SD intensity” at portal and delayed phases and at 15 ± 5 minutes

- **Qualitative evaluation** (*expert reading*) for each available very delayed images (20mn, 1h, 2h) for visualization of the parenchyma enhancement relative to unenhanced fat-suppressed GRE T1 sequence (hyperintense, isointense, hypointense) and nodule enhancement relative to parenchyma

